3.1.1.3 Imaging

All imaging will be sent to the central imaging core laboratory for independent review as soon as possible within 48 hours of acquisition. Further instructions will be provided by the imaging core laboratory in separate guidelines.

Patients will undergo 4 types of imaging during the dose escalation phase: planar whole body (WB) scans, single photon emission computed tomography (SPECT)/CT scans, diagnostic CT scans, and brain MRI scans, as shown in [Table 1](#). Imaging to evaluate the organ/target lesion uptake will be performed after each CAM-H2 administration during the dose escalation phase of

the study for all patients at all dose levels. Dosimetry in tumor lesions, calculated based on consecutive SPECT/CT and planar WB scans, will be performed during Cycle 1. To evaluate disease progression, diagnostic CT scans will be performed in all patients, and brain MRI will only be performed in patients with known brain metastases. Patients with extracranial lesions will be evaluated for progression using RECIST version 1.1. Patients with brain metastases without extracranial lesions will be evaluated for progression using RANO-BM. Patients with extracranial lesions and brain metastases will be evaluated for progression using both RECIST version 1.1 (extracranial lesions) and RANO-BM (brain metastases). Additional details are provided in the Imaging Review Charter.

Table 1. Imaging During the Dose Escalation Phase

Type of Imaging	Cycle 1	Cycles 2, 3, and 4
Planar WB scans for PD distribution [1], evaluation of organ/target lesion uptake, and/or dosimetry	
After each dose (Dose 1 and Dose 2):
 
 • 5 hours (± 1 hour) after CAM-H2 [2]; • 24 hours (± 4 hours) after CAM-H2; • 48 hours (± 4 hours) after CAM-H2; and • 168 hours (± 24 hours) after CAM-H2. 	After each dose (Dose 1 and Dose 2): • 24 hours (± 4 hours) after CAM-H2 [2].
SPECT/CT scans to evaluate organ/target lesion uptake and/or dosimetry	
After each dose (Dose 1 and Dose 2):
 
 • 5 hours (± 1 hour) after CAM-H2; • 24 hours (± 4 hours) after CAM-H2; • 48 hours (± 4 hours) after CAM-H2; and • 168 hours (± 24 hours) after CAM-H2. 	NA

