Diagnostic CT scans to evaluate disease status	
At screening and after Dose 2 only [3]:
 
 • 4 weeks after CAM-H2 at Visit 10 (Week 8); and • Every 8 weeks after Visit 10 (Week 8), as long as the patient had clinical benefit after Cycle 1 [4] and there is no disease progression. 	
After Dose 2 only [3]:
 
 • 4 weeks after CAM-H2 at Week 8; and • Every 8 weeks after Week 8, as long as the patient had clinical benefit after the current cycle [4] and there is no disease progression.
Brain MRI scans to evaluate disease status [5]	
At screening and after Dose 2 only [3]:
 
 • 4 weeks after CAM-H2 at Visit 10 (Week 8); and • Every 8 weeks after Visit 10 (Week 8), as long as the patient had clinical benefit after Cycle 1 [4] and there is no disease progression. 	
After Dose 2 only [3]:
 
 • 4 weeks after CAM-H2 at Week 8; and • Every 8 weeks after Week 8, as long as the patient had clinical benefit after the current cycle [4] and there is no disease progression.

 1. Patients with a negative PD distribution scan will not be treated further, although they will be included in the SAF. An extra patient will then be included in the same cohort as substitute. 2. During Dose 1 of the cycle, the first planar WB scan will also serve as the PD distribution scan. 3. Imaging to evaluate disease status after treatment will start 4 weeks after the last CAM-H2 infusion (Dose 2) of the cycle at Week 8. If a patient cannot receive Dose 2 of a given cycle, his/her imaging to evaluate disease status will start at the theoretical timing for Dose 2 (ie, 4 weeks after Dose 1 of the cycle). 4. Patients without clinical benefit after the current cycle will have another diagnostic CT scan and brain MRI (if indicated) at Week 11, which will be EOT. 5. Brain MRI will only be performed in patients with known brain metastases. 		

CT = computed tomography; EOT = End of Treatment; MRI = magnetic resonance imaging; NA = not applicable; PD = pharmacodynamic(s); SAF = Safety Analysis Set; SPECT = single photon emission computed tomography; WB = whole body.
		

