3.1.2.3 Imaging

As in the dose escalation phase, all imaging will be sent to the central imaging core laboratory for independent review as soon as possible within 48 hours of acquisition. Further instructions will be provided by the imaging core laboratory in separate guidelines.

Patients in the dose expansion phase will undergo planar WB scans, SPECT/CT scans, diagnostic CT scans, and brain MRIs, as shown in [Table 2](#). As in the dose escalation phase, imaging to evaluate the organ/target lesion uptake will be performed after each CAM-H2 administration; however, it will be performed less frequently. Imaging to evaluate disease progression will be performed as done in the dose escalation phase (see [Section 3.1.1.3](#)).

Table 2. Imaging During the Dose Expansion Phase

Type of Imaging	Cycle 1	Cycle 2
Planar WB scans for PD distribution and evaluation of organ/target lesion uptake	After each dose (Dose 1 and Dose 2): • 24 hours (\pm 4 hours) after CAM-H2 [1].	After each dose (Dose 1 and Dose 2): • 24 hours (\pm 4 hours) after CAM-H2 [1].
SPECT/CT scans to evaluate organ/target lesion uptake	After each dose (Dose 1 and Dose 2): • 24 hours (\pm 4 hours) after CAM-H2.	NA
Diagnostic CT scans to evaluate disease status	At screening and after Dose 2 only [2]: • 4 weeks after CAM-H2 at Visit 10 (Week 8); and • Every 8 weeks after Visit 10 (Week 8), as long as the patient had clinical benefit after Cycle 1 [3] and there is no disease progression.	After Dose 2 only [2]: • 4 weeks after CAM-H2 at Visit 19 (Week 8); • At Visit 20 (Week 11/EOT); and • Every 8 weeks after Visit 20 (Week 11), as long as there is no disease progression.
Brain MRI scans to evaluate disease status [4]	At screening and after Dose 2 only [2]: • 4 weeks after CAM-H2 at Visit 10 (Week 8); and • Every 8 weeks after Visit 10 (Week 8), as long as the patient had clinical benefit after Cycle 1 [3] and there is no disease progression.	After Dose 2 only [2]: • 4 weeks after CAM-H2 at Visit 19 (Week 8); • At Visit 20 (Week 11/EOT); and • Every 8 weeks after Visit 20 (Week 1), as long as there is no disease progression.

1. During Dose 1 of the cycle, the first planar WB scan will also serve as the PD distribution scan.

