- Administer saline 0.9% infusion, starting 30 minutes prior to study drug administration and continuing for up to 3 hours after, at a rate of 200 to 300 mL/hour;
- Administer an amino acid solution beginning 30 minutes prior to study drug administration and ending 3 hours after study drug administration, at a rate of 250 to 500 mL/hour;
- Administer study drug via slow IV infusion, ie, administer using a shielded infusion device over approximately 3 to 30 minutes, depending on the volume to be injected; and
- Perform a planar WB scan and SPECT/CT scan at 5 (± 1) hours, 24 (± 4) hours, and 48 (± 4) hours after study drug administration.

Note: The planar WB scan done at 5 hours will also serve as the PD distribution scan.

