- Administer study drug via slow IV infusion, ie, administer using a shielded infusion device over approximately 3 to 30 minutes, depending on the volume to be injected; and
- Perform a planar WB scan 24 (± 4) hours after study drug administration. The planar WB scan done at this visit will also serve as the PD distribution scan.

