6.3.2.5 Visit 7 (Week 4)

Dose 2 of Cycle 1 will be administered at Visit 7. The following procedures will be performed at Visit 7 (Week 4):

- Admit to radioactive unit for hospitalization prior to study drug administration;

Note: Patients will be admitted during each IV administration for a total of 48 hours. This hospitalization can be shortened if ^{131}I decay and the patient's clearance allow discharge according to the applicable local regulations on radioactive compound exposure.

Note: Before the patient is released, a leaflet containing information on radioprotection rules and general precautions after radiation treatment will be distributed (see [Appendix F](#)).

- Confirm the ingestion of thyroid-blocking drugs at least 24 hours prior to study drug administration;
- Deliver and confirm the ingestion of thyroid-blocking drugs 1 hour prior to study drug administration;
- Deliver and confirm the ingestion of thyroid-blocking drugs 24 and 48 hours after study drug administration;

Note: If the patient is discharged prior to 48 hours, deliver the thyroid-blocking drugs for 48 hours at 24 hours. Patients will still take the thyroid-blocking drugs 48 hours after study drug administration.

- Perform urine hCG testing in all female patients of childbearing potential (ie, ovulating, premenopausal, and not surgically sterile) prior to study drug administration;
- Collect blood to evaluate serum for ADAs and to measure exploratory biomarkers (from patients who have consented to the procedure) prior to study drug administration;
- Assess AEs;
- Perform physical examination prior to study drug administration and at 24 hours after study drug administration;
- Measure vital signs prior to study drug administration and 30 minutes, 5 hours, 24 hours, and 48 hours after study drug administration;
- Perform clinical laboratory tests prior to study drug administration;
- Administer anti-emetic, anti-histamine, and anti-pyretic premedication therapy approximately 30 minutes prior to the start of the amino acid infusion, according to the site's standard operating procedures;
- Administer saline 0.9% infusion, starting 30 minutes prior to study drug administration and continuing for up to 3 hours after, at a rate of 200 to 300 mL/hour;
- Administer an amino acid solution beginning 30 minutes prior to study drug administration and ending 3 hours after study drug administration at a rate of 250 to 500 mL/hour;

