- t. This hospitalization can be shortened if ^{131}I decay and the patient's clearance allow discharge according to the applicable local regulations on radioactive compound exposure. Before the patient is released, a leaflet containing information on radioprotection rules and general precautions after radiation treatment will be distributed (see [Appendix F](#)).
- u. Anti-emetic, anti-histamine, and anti-pyretic premedication should be administered approximately 30 minutes before the start of the amino acid infusion, according to the site's standard operating procedures. In the case of severe nausea or vomiting during the study drug or amino acid infusion, additional anti-emetic therapy can be initiated as per local procedures.
- v. Saline 0.9% infusion will be initiated 30 minutes prior to study drug administration and continued for up to 3 hours after, at a rate of 200 to 300 mL/hour.

- w. Administration of the amino acid solution should be initiated 30 minutes prior to study drug administration, with an infusion rate of 250 to 500 mL/hour. Amino acid solution infusion should be continued for 3 hours after study drug administration. Rates lower than 320 mL/hour are not recommended for commercial solutions. The amino acid solution will be prepared as a compounded product, in compliance with the hospital's sterile medicinal product preparation good practices and according to the composition specified in [Table 5](#).
- x. This will be injected via a slow IV infusion. The study drug will be administered using a shielded infusion device over approximately 3 to 30 minutes, depending on the volume to be injected.
- y. Acceptable time windows for the imaging to evaluate the organ/target lesion uptake are provided in [Table 2](#).
- z. During Dose 1 of the cycle, the planar WB scan will serve as the PD distribution scan.
- aa. All patients will undergo pre-treatment imaging for eligibility and baseline at V1 with a diagnostic CT scan for RECIST v1.1 and a brain MRI scan for RANO-BM. Imaging to evaluate disease status after treatment will start 4 weeks after the last CAM-H2 infusion (Dose 2) of the cycle at V10 (Week 8). If a patient cannot receive Dose 2 of a given cycle, his/her imaging to evaluate disease status will start at the theoretical timing for Dose 2 (ie, 4 weeks after Dose 1 of the cycle).

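### In expansion the 24 h planar scan after Cycle 1 Dose 1 is named the PD distribution scan, but escalation's rule to stop treatment when that scan is negative is not carried over

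*Combined protocol and SAP*

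**What the plan says.** **Escalation.** The planar-scan row of Table 1 (Section 3.1.1.3; Table S2 in the synopsis is the same) carries footnote 1: "Patients with a negative PD distribution scan will not be treated further, although they will be included in the SAF". The footnote goes on to require a substitute in the cohort, and Section 3.1.1.2 repeats the replacement. In Cycle 1 the relevant scan is the early one (Section 6.2.2.1): "The planar WB scan done at 5 hours will also serve as the PD distribution scan".

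**Expansion.** The corresponding row of Table 2 (Section 3.1.2.3; Table S3 in the synopsis) reads "Planar WB scans for PD distribution and evaluation of organ/target lesion uptake", with the scan at 24 h after each dose. Its footnote 1 and the Visit 3 text (Section 6.3.2.1) identify the scan after Dose 1 as the PD (pharmacodynamic) distribution scan. Table 9 footnote z in Appendix A says the same: "During Dose 1 of the cycle, the planar WB scan will serve as the PD distribution scan". None of these adds a consequence. Section 3.1.2.3 points back to the escalation imaging section for one purpose only: "Imaging to evaluate disease progression will be performed as done in the dose escalation phase".

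**The concern.** The PD distribution scan shows whether the radioligand has reached its target. In escalation the protocol treats a negative result as reason enough to give no more drug. Eligibility (Section 4.1) requires HER2-positive disease but no uptake scan, so in expansion the scan after Dose 1 is the first planned look at uptake. It is given the same name as in escalation but has no decision attached.

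At stake is a second therapeutic administration, with its kidney dose, radioactive-unit stay and contact restrictions, in a patient whom the escalation rule would have stopped. Most patients treated at the recommended dose will be in expansion, at roughly 10 to 15 sites, so the same result could also be handled differently from site to site.

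**Working it through.** **1. Is there an action anywhere in the expansion text?**

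| Place | Content on a negative scan |
|---|---|
| Table 1 / Table S2, footnote 1 (escalation) | Stop treatment; keep in the SAF; add a substitute |
| Table 2 / Table S3, footnote 1 (expansion) | Names the scan; no action |
| Section 6.3.2.1, Visit 3 | Names the scan; no action |
| Appendix A, Table 9 footnote z | Names the scan; no action |
| Section 3.1.2.3, reference back to 3.1.1.3 | Disease-progression imaging only |
| Section 3.1.5.2, dose modifications | Toxicities only |
| Section 3.1.5.3, missed doses | Production problems and circumstances unrelated to study drug or procedures |
| Section 4.3, withdrawal | Stopping permitted on general grounds; this result not listed |
| Section 9, statistics | Nothing |

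The only difference between the phases is that the footnote is present in one and absent in the other.

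**2. Is the stop only a dose-finding device?** Section 3.1.1.2 ties *replacement* to having full-cycle safety data for escalation decisions. It does not give that reason for *stopping*. Stopping is what produces the incomplete cycle that replacement then repairs, so the dose-finding purpose does not explain the stop.

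**3. Kidney dose from one further administration.** Inputs: 34.9 ± 2 mGy/mCi and the 23 Gy limit (Section 1.3.2); activities per dose of 50, 100, 150 and 200 mCi (Table 3).

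Reproducing the protocol's figures first:
- 34.9 mGy/mCi × 400 mCi = 13.96 Gy, matching the stated 14 Gy for 2 × 200 mCi.
- 23,000 mGy ÷ 34.9 mGy/mCi = 659 mCi, as stated.

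Per administration, dose = 34.9 mGy/mCi × activity:

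| Level | Activity | Mean | With ± 2 mGy/mCi | Share of 23 Gy |
|---|---|---|---|---|
| 1 | 50 mCi | 1.745 Gy | 1.645 to 1.845 Gy | 7.6% |
| 2 | 100 mCi | 3.49 Gy | 3.29 to 3.69 Gy | 15.2% |
| 3 | 150 mCi | 5.235 Gy | 4.935 to 5.535 Gy | 22.8% |
| 4 | 200 mCi | 6.98 Gy | 6.58 to 7.38 Gy | 30.3% |

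**4. How many patients?** The negative-scan rate is not given, so this is assumption only. Taking the planned total of 52 at the chosen dose, expansion contributes all 52, or 52 − 9 = 43 if up to 9 escalation patients (a cohort of up to 6 plus 3 more) count towards it. At an assumed 5% negative, 0.05 × 43 = 2.2 to 0.05 × 52 = 2.6 patients. At an assumed 20%, 0.20 × 43 = 8.6 to 0.20 × 52 = 10.4 patients.

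**5. Is there time to use the result?** Images go to the core laboratory within 48 h, and Dose 2 is 28 days after Dose 1. That leaves 28 d − (24 h + 48 h) = 25 days. At the limits of the windows (Dose 2 three days early, scan at 28 h), it is 28 d − 3 d − (28 h + 48 h) = 21.8 days.

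**The case against.** **The difference may be deliberate.** In Cycle 1 the two phases use different scans, 5 h and 24 h. With the 12 h biological half-life reported in healthy subjects (Section 1.2), whole-body retention before physical decay would be 2^(−5/12) = 75% at 5 h and 2^(−24/12) = 25% at 24 h. A sponsor might reasonably not want a later, lower-count planar image to force a stop. This is a fair argument for confirming a negative scan before acting on it. The protocol does not make the argument, however, and does not say that expansion patients are treated whatever the scan shows.

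**Other documents may cover it.** The Imaging Review Charter and the core-laboratory guidelines are not available here. They may govern how the scan is read. The protocol does not point to them for this rule, and it puts the escalation rule in its own text.

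**The investigator can stop the patient.** Section 4.3 allows this but does not require it.

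**The kidney figures can look alarming.** A full cycle at the highest level is predicted at 14 Gy, below the limit, and expansion Cycle 2 has its own 23 Gy condition. A reader might infer that the missing rule takes patients over the limit within the cycle; the predictions do not support that.

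Two further readings are tempting:

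- *That the unconditional scheduling of Dose 2 shows the phases differ.* It does not. Expansion Visit 7 says "Dose 2 of Cycle 1 will be administered at Visit 7", but escalation Visit 7 (Section 6.2.2.5) says the same, and both phases state that every patient receives at least one cycle.
- *That a stop should also be mandatory at expansion Visit 16, because escalation applies it to the 24 h scan in Cycles 2 to 4.* That reach rests on a marker on a row label, "Planar WB scans for PD distribution [1], evaluation of organ/target lesion uptake, and/or dosimetry", together with the Week 0 text for those cycles, "The planar WB scan done at this visit will also serve as the PD distribution scan". The substitution half of the footnote makes sense only for Cycle 1. More importantly, Cycle 2 patients already have clinical benefit. A responder with shrunken lesions could have a negative scan, and a mandatory stop would end a treatment that is working. Table 2 also has no Cycle 2 SPECT/CT with which to confirm the result.

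**Conclusion.** The gap is real for expansion Cycle 1. The protocol names a PD distribution scan, gives it a stopping consequence in escalation, and attaches no consequence to it in expansion. As written, a patient with a negative scan proceeds to Dose 2, with a predicted further 1.7, 3.5, 5.2 or 7.0 Gy to the kidneys at levels 1 to 4.

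The size rests on mean predictions extrapolated from non-human primates for males, the more sensitive sex. How many patients would be affected cannot be estimated from the documents. A negative scan is defined in neither phase, so no existing criterion can be assumed to transfer. The conclusion does not extend to a mandatory stop in Cycle 2. A reader might also infer that the interim response-rate rule needs rewording. That is a separate question, and Section 9.1 already keeps every dosed patient in the FAS.

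**What to change.** Add to Tables 2 and S3, and repeat at expansion Visit 7 (Section 6.3.2.5):

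> Patients whose Cycle 1 PD distribution scan is negative, confirmed on the SPECT/CT taken at the same 24 h time point, will not receive Dose 2; they remain in the SAF and FAS and enter long-term follow-up. The scan result must be available before Dose 2.

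Replacement stays at the sponsor's discretion under Section 4.3. Table 2 footnote 2 already sets disease-status imaging for a patient who misses Dose 2. If the sponsor does intend to treat regardless of the scan in expansion, a sentence saying so, with the reason, would close the gap instead.

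**Cost.** No scan or visit is added, since the 24 h SPECT/CT is already scheduled in expansion Cycle 1. The protocol states no turnaround for the central read, so one must be agreed with the core laboratory; about 22 to 25 days are available. The main downside is that a patient with a falsely negative 24 h scan would lose Dose 2. The SPECT/CT confirmation limits that risk but does not remove it.

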3.1.2 Dose Expansion Phase

3.1.2.1 Screening

Following the completion of the dose escalation phase and determination of the MTD or RDP2, the study will be expanded so that a total of at least 52 patients will be exposed to the dose chosen to be taken forward. Of the included patients with advanced/metastatic breast cancer, at least 10 to 12 patients should have measurable brain metastases. The number of patients with gastric or GEJ cancer and brain metastases is not pre-set.

Patients will be screened for study eligibility over 2 different study visits (Visit 1 and Visit 2) in the 29 days prior to dosing (ie, Day -28 to Day 0 of Cycle 1). Visit 2 should occur preferably within the 14 days prior to study drug administration (Visit 3). All patients will undergo pre-treatment imaging for eligibility and baseline at Visit 1 with a diagnostic CT scan for RECIST version 1.1. Patients with known brain metastases will undergo a brain MRI scan, in addition to the diagnostic CT, for RANO-BM.

As in the dose escalation phase, the screening period may be extended up to an additional 2 weeks upon Sponsor approval in certain exceptional cases (eg, to allow for a repeat blood draw or to assess previously unavailable imaging results) following a discussion between the Principal Investigator, Medical Monitor, and Sponsor.

3.1.2.2 CAM-H2 administration

In the dose expansion phase of the study, the patients will be given the RDP2 determined in the dose escalation phase. Similar to the dose escalation phase, all patients will receive at least 1 cycle of CAM-H2. Patients with CB may receive up to 2 cycles of CAM-H2, as long as the cumulative kidney dose remains <23 Gy (based on the dosimetry results during Cycle 1 of dose escalation), each cycle given as 2 IV administrations, 4 weeks apart. However, if a patient misses a dose of study drug due to study drug production problems or due to other circumstances (in certain cases), the interval between doses may be extended up to 6 weeks (see [Section 3.1.5.3](#)).

Patients will be admitted to a radioactive unit for hospitalization during each IV administration for a total of 48 hours. This hospitalization can be shortened if ^{131}I decay and the patient's clearance allow discharge according to the applicable local regulations on radioactive compound exposure. Ancillary treatments to be given with CAM-H2 include thyroid-blocking drugs, premedication therapy (anti-emetic, anti-histamine, and anti-pyretic therapy), saline infusion, and amino acid infusion.

Cycle 1 will consist of the following:

- Dose 1 of CAM-H2: Visit 3 (Week 0);
- Safety Follow-Up Period: Visit 4 (Week 1), Visit 5 (Week 2), and Visit 6 (Week 3);
- Dose 2 of CAM-H2: Visit 7 (Week 4); and
- Safety Follow-Up Period: Visit 8 (Week 5), Visit 9 (Week 6), Visit 10 (Week 8), and Visit 11 (Week 11) (EOT Visit or Cycle 2 eligibility assessment).

If the patient has CB, an additional cycle may be initiated within 2 weeks after the EOT Visit of Cycle 1, once the necessary Visit 11 (Week 11) safety follow-up assessments have been completed

and reviewed. If the patient does not have CB, no further treatment will be administered and the patient will enter the long-term follow-up period.

If the patient has CB, Cycle 2 will then be initiated as follows:

- Dose 1 of CAM-H2: Visit 12 (Week 0);
- Safety Follow-Up Period: Visit 13 (Week 1), Visit 14 (Week 2), and Visit 15 (Week 3);
- Dose 2 of CAM-H2: Visit 16 (Week 4); and
- Safety Follow-Up Period: Visit 17 (Week 5), Visit 18 (Week 6), Visit 19 (Week 8), and Visit 20 (Week 11) (EOT Visit).

